PM104-A-004-05§ (1-hour Day 1, 8 and 15 q4wk)	2 (Europe)	49	2.0	1.5	
 Dose level 7 (2 mg/m², RD): grade 4 lipase increase. Dose level 8 and 9 (2.5 and 3.0 mg/m², MTD): grade 3/4 asthenia, grade 3 nausea, grade 1 neutropenia and thrombocytopenia leading to two missing infusions, grade 3 febrile neutropenia, grade 3 anemia, grade 4 neutropenia, grade 4 thrombocytopenia and grade 4 leukopenia. 	Closed (65)

* Additionally, grade 4 troponin I increase without cardiac symptoms or ECG alterations was also reported (no DLT).

**The highest dose level reached up to December 2008 was 3.5 mg/m² (three patients enrolled).

***Recommended dose not achieved; dose intensity is expected to be 1.3 mg/m²/week.

****Prematurely closed due to low recruitment and unpractical dosing schedule.

†The highest dose level reached was 0.475 mg/m²/day.

§This schedule is the same than that used in the current phase II study: PM104-B-001-09.

In all studies, escalating dose cohorts are 1 to 3-6 patients per dose level. DLT, dose-limiting toxicities; ECG, electrocardiogram; MTD, maximum tolerated dose; RD, recommended dose; q3wk, every 3 weeks; q4wk, every 4 weeks

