7.2.2. Criteria for Treatment Continuation

In order to be re-treated on Day 1 of a new cycle, the patients will have to fulfill the same criteria as at study entry ([Table 11](#)).

If these criteria are not met on Day 1 of a new cycle, treatment administration should be delayed up to two weeks and reevaluated weekly. The new cycle will start upon recovery of these parameters, according to these same criteria.

A maximum delay of two weeks is allowed for recovery from drug-related AEs. If toxicities have not recovered after a maximum delay of two weeks, the patient should discontinue the treatment. In the event of obvious clinical benefit, the patient will remain on treatment only after having discussed and agreed upon the case with the Sponsor, and upon recovery of all parameters according to the aforementioned criteria.

In order to be re-treated on Day 8 and Day 15 of each cycle, the patients will have to fulfill the criteria also described in [Table 11](#). If these criteria are not met on Day 8 or Day 15, the respective infusion will be skipped. If both Day 8 and Day 15 infusions cannot be administered for any reason, the patient should discontinue the treatment, except in the event of obvious clinical benefit, in which case the patient will be allowed to remain on treatment only after having discussed and agreed upon the case with the Sponsor, and upon subsequent recovery of all parameters according to the aforementioned criteria.

Table 11. Criteria for continuation of treatment.

Parameter	Value on Day 1	Value on Day 8/15
Platelet count	$\geq 100 \times 10^9/l$	$\geq 75 \times 10^9/l$
Hb	≥ 9 g/dl	≥ 9 g/dl
ANC	$\geq 1.5 \times 10^9/l$	$\geq 1.0 \times 10^9/l$
AP	$\leq 2.5 \times$ ULN ($\leq 5 \times$ ULN if bone metastases)	$\leq 2.5 \times$ ULN ($\leq 5 \times$ ULN if bone metastases)
ALT, AST	$\leq 2.5 \times$ ULN ($\leq 5 \times$ ULN if hepatic metastases)	$\leq 2.5 \times$ ULN ($\leq 5 \times$ ULN if hepatic metastases)
Total bilirubin	$\leq 1.5 \times$ ULN*	$\leq 1.5 \times$ ULN*
Calculated creatinine clearance (using Cockcroft and Gault formula)	≥ 30 ml/min**	≥ 30 ml/min**
Other non-hematological related events, including renal function (except alopecia and/or vomiting in patients not receiving optimal antiemetic prophylaxis).	NCI-CTCAE grade ≤ 1 (\leq grade 2 in case of asthenia).	NCI-CTCAE grade ≤ 1 (\leq grade 2 in case of asthenia).

[figure not shown]
*Unless due to Gilbert's syndrome.

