Relative dose intensity (%)				

12.1.2 Dose delays.

Table 12.1.2. 1. Dose delay.

	N	%
Number of patients treated		
Number of patients with any dose delay		
Number of cycles administered		
Number of cycles susceptible to be delayed		
Patients with		
No delays		
1 cycle delayed		
2 cycles delayed		
≥ 3 cycles delayed		
Number of cycles with dose delay*		

Programming Notes: Percentage is based on number of cycle susceptible to be delayed.

* Denominator = Number of cycles susceptible to be delayed.

Table 12.1.2. 2. Dose delay according to their relationship to study drug.

	Treatment related**		Non – Treatment related	
	N	%	N	%
Patients with				
No delays				
1 cycle delayed				
2 cycles delayed				
≥ 3 cycles delayed				
Number of cycles with dosing delay				

Programming Notes:

* Denominator = Number of cycles susceptible to be delayed.

** Hematological reason / Non hematological reason.

Table 12.1.2. 3. Length of dose delay.

	Treatment related*		Non – Treatment relat		Total	
	N	%	N	%	N	%
Length of delay						
1 – 7 days						
7 – 14 days						
> 14 days						

Programming Notes:

* Denominator = Number of cycles susceptible to be delayed.

** Hematological reason / Non hematological reason.

Table 12.1.2. 4 . Dose delay and reason by cycle.

	Cycle 2		Cycle 3		...		Total	
	N	%	N	%	N	%	N	%
Number of delays								
Treatment related*								
Hematological reason								
Non hematological reason								
Non Treatment related*								

Programming Notes: * Denominator = Number of cycles susceptible to be delayed.

Listing 12.1.2. 5. Listing of patient with dose delay.

Patient ID	Cycle	Reason of delay	Comments	Delay (days)

12.1.3 Dose reduction.

Note: All dose reductions will be considered and described, specifying the reason for reduction (hematological toxicity, non hematological toxicity or other causes not due to study drug).

Table 12.1.3. 1 Dose reduction.

	N	%
Number of patients treated		
Number of patients with dose reduced		
Number of cycles administered		
Patients with		
N° reductions		
1 cycle reduction		
2 cycle reductions		
≥ 3 cycle reductions		
Number of cycles with dose reduction		

Programming Notes: Percentage is based on number of cycle susceptible to be reduced.

Table 12.1.3. 2 Dose reduction according to their relationship to study drug.

	Treatment related**		Non – Treatment related	
	N	%	N	%
Patients with				
N° reductions				
1 reduction				
2 reductions				
≥ 3 reductions				
Number of cycles with dose reduction*				

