Programming Notes:* Denominator = Number of cycles susceptible to be reduced.
** Hematological reason / Non-hematological reason.

Table 12.1.3. 3 Dose reduction and reason by cycle.

	Cycle 2		Cycle 3		...		Total	
	N	%	N	%	N	%	N	%
Number of patients								
Number of delays								
Treatment related*								
Hematological reason								
Non hematological reason								
Non Treatment related*								

Programming Notes:* Denominator = Number of cycles susceptible to be reduced.

Listing 12.1.3. 4 Patient with dose reduction.

Patient ID	Cycle	Reason of reductio	Comments	Reduction (%)

12.1.4 Skipped doses.

Table 12.1.4. 1 Skipped doses.

	N	%		
Number of patients treated with at least 2 infusions				
Number of patients with any skipped doses				
Number of patients with any skipped doses (drug related)				
Number of cycles administered				
Number of cycles susceptible to have any omission				
Number of cycles with at least one skipped dose (drug related)				
Day 8				
Day 15				
Day 8+15				
	Treatment related**		Non – Treatment related	
	N	%(of all cycles)	N	%(of all cycles)
Day 8				
Day 15				
Day 8+15				

Listing 12.1.4.3. Listing of patients with skipped doses.

Patient ID	Cycle/infusion (skipped dose)	Reason (drug related/other)	Comments
------------	----------------------------------	-----------------------------	----------

12.2 Toxicity.

12.2.1 Adverse events.

Table 12.2. 1 Drug related adverse events. Worst case per patient.

Table 12.2. 2 Drug related adverse events occurring in > 10% of all patients. Worst case per patient.

Table 12.2. 3 All adverse events regardless relationship. Worst case per patient.

Table 12.2. 4 All adverse events regardless relationship occurring in > 10% of all patients. Worst case per patient.

Table 12.2. 5 Drug related adverse events. Worst case per cycle.

Table 12.2. 6 Drug related adverse events occurring in > 10% of all cycles. Worst case per cycle.

Table 12.2. 7 All adverse events regardless relationship. Worst case per cycle.

Table 12.2. 8 All adverse events regardless relationship occurring in > 10% of all cycles. Worst case per cycle.

System Organ Class/ Preferred Term	Grade 1		Grade 2		Grade 3		Grade 4		Total	
	N	%	N	%	N	%	N	%	N	%
System Organ Class 1 Preferred Term 1										
System Organ Class 2 Preferred Term 1										

* Percentages are based on the safety population. Table shows number of distinct patients with events.

12.2.2 Serious toxicity rate.

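### SAP exposure tables: the delay and reduction notes divide patient counts by cycles, a 7-day delay falls in two classes, and the skipped-dose table has no clear patient denominator

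*SAP*

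**What the plan says.** SAP 5.2 places dose delays, modifications and omissions under the secondary safety endpoint. SAP 7.3 refers them to the table shells of Appendix III (section 12).

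- **Delays, Table 12.1.2.1.** The rows include patients treated, patients with any delay, and patients with none, 1, 2 or at least 3 delayed cycles, alongside cycle counts. The general programming note reads "Percentage is based on number of cycle susceptible to be delayed". A second note, marked with an asterisk, gives the same denominator for the row that counts delayed cycles.
- **Reductions, Table 12.1.3.1.** The mix of patient and cycle rows is similar. The only note is "Percentage is based on number of cycle susceptible to be reduced". That cycle count is not a row of the table and is not defined.
- **Length of delay, Table 12.1.2.3.** The classes are 1 to 7 days, 7 to 14 days and more than 14 days.
- **Skipped doses, Table 12.1.4.1.** The first row is "Number of patients treated with at least 2 infusions", where the delay and reduction tables begin with all patients treated. Below it come "Number of patients with any skipped doses", the drug-related version of that row, and "Number of cycles susceptible to have any omission". No note gives a denominator for the patient rows. The lower block (Day 8, Day 15, both) is labelled as a percentage of all cycles.

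Two other provisions matter. SAP 4.1.2 admits to the safety population anyone with one complete or partial infusion. Protocol 7.2.2 says "If both Day 8 and Day 15 infusions cannot be administered for any reason, the patient should discontinue the treatment", with an exception for obvious clinical benefit agreed with the sponsor.

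**The concern.** A percentage needs a numerator drawn from its denominator. Patients counted over cycles give a figure that is neither the share of patients affected nor the share of cycles affected, and the patient categories need not add to 100%.

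The overlap at day 7 falls on a likely value. When the Day 1 criteria are not met, Protocol 7.2.2 says "treatment administration should be delayed up to two weeks and reevaluated weekly", so delays will tend to cluster at one week.

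In the skipped-dose table, the sole patient total is defined by the number of infusions received, which is itself affected by skipping. A patient given Day 1 of Cycle 1 who then misses both later doses and stops has had one infusion. She is a treated patient with the heaviest possible first-cycle omission, yet she is outside that total.

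At stake is the description of how well the Day 1, 8 and 15 schedule was delivered.

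**Working it through.** The shells are empty, so the plan gives no figure to reproduce. The check reads the notes literally and shows what they would print. All patient and cycle counts below are assumptions; 30 is the Group 1 target from Protocol 10.1, which counts evaluable patients, so the number treated may be higher.

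**1. Patient rows over cycles (delays).** Let N patients receive a mean of m cycles. Assume that every cycle after Cycle 1 is susceptible to delay. Then susceptible cycles S = N(m − 1). The patient categories (none, 1, 2, at least 3) contain N patients in all, so they add to N/S = 1/(m − 1), whatever N is. With N = 30 and 6 patients with any delay, the share of patients is 6/30 = 20.0%.

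| Mean cycles m | S | Any delay as printed (6/S) | Sum of patient categories (30/S) |
|---|---|---|---|
| 1.5 | 15 | 40.0% | 200% |
| 2 | 30 | 20.0% | 100% |
| 3 | 60 | 10.0% | 50% |
| 4 | 90 | 6.7% | 33.3% |
| 6 | 150 | 4.0% | 20% |

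The printed figure is too high below a mean of 2 cycles, right at 2 and too low above it.

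**2. Reductions.** The denominator is undefined. If it means cycles after the first, the sums above apply. If it means every cycle given, the categories add to N/(Nm) = 1/m: 66.7% at m = 1.5, 50% at 2, 33.3% at 3.

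**3. Length of delay.** A delay of exactly 7 days satisfies both of the first two classes. The shell does not say which one takes it.

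**4. Skipped doses.** Suppose 30 patients are treated. Let k of them receive only Day 1 of Cycle 1, miss both later doses and stop. Let 6 of the others skip at least one dose. Three percentages are open to a programmer:

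| k | All treated, (6 + k)/30 | At least 2 infusions in both parts, 6/(30 − k) | All skippers over the restricted total, (6 + k)/(30 − k) |
|---|---|---|---|
| 1 | 23.3% | 20.7% | 24.1% |
| 2 | 26.7% | 21.4% | 28.6% |
| 3 | 30.0% | 22.2% | 33.3% |
| 5 | 36.7% | 24.0% | 44.0% |

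The gap between the first two columns runs from 2.6 points (k = 1) to 12.7 points (k = 5). In the third column the numerator is not contained in the denominator.

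**5. Companion shells.** In Table 12.1.3.2 the cycle denominator is tied by an asterisk to the cycle row only, which is correct. In Table 12.1.2.2 the same kind of note exists, but no row carries the asterisk.

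**The case against.** The strongest reply is that this is loose wording in shells whose intent is clear. Table 12.1.2.1 begins with patients treated and has a separate asterisked note for its cycle row, which suggests that patient rows were meant over patients. That is probably the intent, but the general note then has no job except to govern the other rows. Table 12.1.3.1 has no asterisked note at all, so its only instruction is the wrong one for patient rows. Exact delays in days appear in Listing 12.1.2.5, so the day-7 overlap can be resolved from the data. It still has to be settled for the table.

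On skipped doses the reply is stronger. A reader might infer that the SAP excludes patients who stop after one infusion. The documents do not say so. The two-infusion row has its own count and percentage and could be purely descriptive. The lower block is over all cycles, so a Cycle 1 with only Day 1 given can be counted there with its Day 8+15 omission. Listing 12.1.4.3 sets no minimum number of infusions. SAP 7.1 tabulates reasons for stopping by number of cycles received. Relative dose intensity would also show such a patient: one infusion of 2 mg/m² over 4 weeks is 0.5 mg/m²/week against an intended 1.5, or 33%. Patients kept on under the clinical-benefit exception can reach two infusions in any case. All of this stands. What remains is that the patient rows have no stated denominator and that the only total offered leaves these patients out.

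A reader might also point to phase I, where "grade 1 neutropenia and thrombocytopenia leading to two missing infusions" was listed as dose-limiting on this schedule. Protocol Table 6 lists it at 2.5 and 3.0 mg/m², not at the 2 mg/m² used here, so it says nothing direct about how often this will occur.

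**Conclusion.** The point holds for the tables named. The notes to Tables 12.1.2.1 and 12.1.3.1, read as written, give wrong percentages for patient rows. The size depends on mean cycles per patient and, for delays, on the assumption that every cycle after the first is susceptible. Table 12.1.2.3 has overlapping classes. Table 12.1.4.1 has an unstated patient denominator and an unsuitable candidate for it; the 2.6 to 12.7 point range rests entirely on assumed counts.

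The documents do not support concluding that the tables will make the schedule look easier to deliver. The delay error changes direction at a mean of 2 cycles, and the skipped-dose figure can come out below or above the all-treated rate depending on how the row is programmed. Response rate, the two-stage decisions and the toxicity stopping rule do not use these tables and are unaffected. Since delays, modifications and omissions are named under a secondary endpoint, the correction is still worth making before programming.

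**What to change.** - **Tables 12.1.2.1 and 12.1.3.1:** base patient rows on patients treated and cycle rows on susceptible cycles. For delays, patients with at least one cycle susceptible to delay is an acceptable alternative base if it is stated. Define what makes a cycle susceptible to delay and to reduction.
- **Table 12.1.2.2:** attach the existing asterisk to the cycle row. Leave Table 12.1.3.2 as it is.
- **Table 12.1.2.3:** use 1–7, 8–14 and more than 14 days.
- **Table 12.1.4.1:** make the first row all patients treated and use it as the denominator of the patient rows. Count every cycle whose Day 1 infusion was given, including Cycle 1 of patients who then stop, and state the definition of a cycle susceptible to omission.

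The cost is edits to shells and programming notes, with no new data. The reported skipped-dose rate may be slightly less favourable than under the restricted base.

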4.1.2 Safety population

All patients who have received at least one complete or partial infusion of PM00104 infusion will be included in the safety analysis.

5 Endpoints

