7.5 Statistical methodology for safety

Descriptive statistics, tabulation and graphic representation will be used for the evaluation of safety by tumor type in this phase II study, as described in section 12 (Appendix III).

If the safety profile of PM00104 is similar in both study groups (endometrial and cervical cancer), a pooled analysis for all included patients regardless its tumor type could be performed for safety.

Adverse events will be graded according to NCI-CTCAE version 3.0. The incidence and grade of adverse events and laboratory abnormalities will be calculated considering the most severe grade per patient and cycle.

Descriptive statistics will be used to present the profiles of drug-related adverse events, drug-related deaths, SAE and drug-related treatment discontinuation and the observed grade 1-4 toxicities, per patient and per cycle.

The shift of severity grades from baseline to the worst occurrence during treatment will be tabulated. The time to onset and recovery from neutrophils, platelets and hepatic enzymes elevations will be illustrated by means of descriptive statistics.

Database listings of deaths and serious adverse events will be provided, including at least date of onset and resolution (if applicable), severity, relationship to study drug, significant consequences and actions taken.

PS, weight gain – loss and LVEF measurements evolution during the study will be summarized by frequency tabulation.

See section 12 (Appendix III) for further details on the safety analysis.

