7.6 Missing values management

In case of missing values in the determination of protocol deviations (i.e. time from last anticancer treatment to start of treatment with PM00104) the most conservative approach will be taken for the evaluation.

If a date is missing, the worst case will be taken into account when calculating the difference between two dates. In such a case, this will be specified in the table footnote.

The cycles with missing information regarding laboratory values or adverse events will be subtracted from the denominator of the tables.

As regards of the analysis of Time to Progression, in case of more than one missing tumor scan between the last evaluation without progression and the documentation of progressive disease, the time to progression will be censored at the day of the last tumor evaluation without progression.

8 Pharmacokinetic (PK) and pharmacogenomic (PGx) evaluation

These analysis will be described in two different documents not included in this SAP.

9 Statistical software

Oracle Clinical will be used for double data entry and clinical data management.

SAS v8.2 will be used for all the statistical analysis.

TABLES, LISTINGS AND FIGURE SHELLS

NOTE: All tables, listings and figures described in this section will be duplicated in two different groups. First, patients with endometrial cancer (group 1) and secondly, patients with cervical cancer (group 2).

If appropriate, a pooled analysis for all included patients regardless its tumor type (group 1 + group 2) could be performed for Safety as in Sections 12.2 and 12.3.

Each particular table, listing and figure will have a comprehensive header and/or footnotes, identifying the group of treatment and/or relevant specifications.

10 Appendix I. Patients disposition.

10.1 General characteristics.

10.1.1 Patients treated, eligible and evaluable.

Table 10.1.1. 1. Patients accrual by institution.

	Institution 1		Institution 2		Institution ..		Total	
	N	%	N	%	N	%	N	%
	N-included							
N-treated								

Table 10.1.1. 2. Disposition of patients.

Event	Date
Date first consent	
Date first dose of first patient	
Date last consent	
Date first dose of last patient	
Date last dose	
Last follow up date	

Table 10.1.1. 3. Number of patients evaluable for analysis.

	N. evaluable for efficacy		N. evaluable for safety		Total	
	N	%	N	%	N	%
N-included						
N-treated						

10.1.3 Protocol deviations.

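### One footnote counting distinct patients serves all eight adverse-event tables in SAP 12.2.1 and contradicts the four that are meant to be per cycle (Tables 12.2.5–12.2.8)

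*SAP*

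**What the plan says.** SAP section 12.2.1 (Adverse events) names Tables 12.2.1 to 12.2.8 and gives one shell for all of them, with grade columns, a total column and this footnote: "Percentages are based on the safety population. Table shows number of distinct patients with events". No other adverse-event shell or footnote is given.

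The first four titles ask for the worst case per patient and the last four for the worst case per cycle. Two of the last four also filter terms by frequency:

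- Table 12.2.6: "Drug related adverse events occurring in > 10% of all cycles. Worst case per cycle"
- Table 12.2.8: "All adverse events regardless relationship occurring in > 10% of all cycles. Worst case per cycle"

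Other parts of the SAP bear on the unit:

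- Section 4.1.2 defines the safety population as patients: "All patients who have received at least one complete or partial infusion of PM00104 infusion will be included in the safety analysis".
- Section 7.5 sets the method: "The incidence and grade of adverse events and laboratory abnormalities will be calculated considering the most severe grade per patient and cycle". It also promises descriptive statistics for "the observed grade 1-4 toxicities, per patient and per cycle".
- Section 7.6 sets the missing-data rule: "The cycles with missing information regarding laboratory values or adverse events will be subtracted from the denominator of the tables".
- The note before the shells says: "Each particular table, listing and figure will have a comprehensive header and/or footnotes".

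The protocol's safety analysis section (10.3.2) names the patients to be included but no per-cycle denominator, so the SAP alone settles the question.

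**The concern.** A count of distinct patients over a population of patients is a patient incidence, whatever the table title says. If Tables 12.2.5–12.2.8 are programmed from their footnote, the per-cycle adverse-event rates promised in SAP 7.5 are not reported. In Tables 12.2.6 and 12.2.8 a term would be selected on one unit and printed on another. A reader of the study report would take the percentages as shares of cycles.

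**Working it through.** The plan states no figure on this point, so there is none to reproduce. The check compares the texts and then illustrates the consequence.

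**1. The texts side by side**

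| Source | Unit counted | Denominator |
|---|---|---|
| Shared footnote, SAP 12.2.1 | distinct patients | safety population, which is patients (4.1.2) |
| Titles of Tables 12.2.1–12.2.4 | patient | consistent with the footnote |
| Titles of Tables 12.2.5–12.2.8 | cycle | not stated in the title |
| Filter in Tables 12.2.6 and 12.2.8 | cycle | all cycles |
| SAP 7.5 | patient and cycle | not stated |
| SAP 7.6 | – | must be cycles, since cycles are subtracted from it |

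The footnote agrees with four tables and conflicts with the other four on the unit counted. It also conflicts with 7.6 on the base: a denominator of patients contains no cycles to subtract.

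**2. A consequence that needs no assumed numbers**

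Tables 12.2.1 and 12.2.5 both cover drug-related events. Under the footnote both count distinct patients over the same population, so for each term the total column of 12.2.5 would repeat that of 12.2.1. In the same way, 12.2.7 would repeat the total column of 12.2.3.

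**3. Illustration on assumed counts**

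Inputs: 30 and 32 patients are the maximum evaluable numbers in SAP 6.1, used here as stand-ins for the safety population. The mean of 2 to 4 cycles per patient is assumed, because the documents do not give one. One term is assumed to occur in 6 patients, in one cycle each.

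Formulas: footnote basis = patients with the event / patients. Cycle basis = cycles with the event / (patients × mean cycles).

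| Patients | Mean cycles | Cycles | Footnote basis | Cycle basis |
|---|---|---|---|---|
| 30 | 2 | 60 | 6/30 = 20.0% | 6/60 = 10.0% |
| 30 | 3 | 90 | 6/30 = 20.0% | 6/90 = 6.7% |
| 30 | 4 | 120 | 6/30 = 20.0% | 6/120 = 5.0% |
| 32 | 2 | 64 | 6/32 = 18.8% | 6/64 = 9.4% |
| 32 | 3 | 96 | 6/32 = 18.8% | 6/96 = 6.25% |
| 32 | 4 | 128 | 6/32 = 18.8% | 6/128 = 4.7% |

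In every row the term exceeds 10% on the footnote basis. In no row does it exceed 10% of cycles.

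**4. Recurrence and the selection rule**

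Let the same 6 of 30 patients have the event in two cycles each, with 90 cycles in all. The cycle rate is 12/90 = 13.3%, so the term qualifies for Table 12.2.6, but the footnote would print it as 6/30 = 20.0%. The footnote figure does not change when recurrence doubles, and recurrence is what a per-cycle table is meant to show.

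**5. Direction**

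If each of N patients has the same number m of cycles and k of them have the event, there are at most k × m event cycles. The cycle rate is then at most (k × m)/(N × m) = k/N, so the footnote figure is never the smaller one. A reversal needs the affected patients to have more cycles than average.

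**The case against.** The strongest reply is that the intended unit is already clear. The titles, the filters, SAP 7.5 and SAP 7.6 all point to cycles, the SAP promises specific headers and footnotes for each table, and an experienced programmer would see a per-patient footnote left under a shared shell. Much of this stands: it is a slip in a table note rather than a deliberate choice of method. It does not remove the conflict. The general promise of footnotes states no count or base, and the one adverse-event footnote actually written explicitly says distinct patients. Programming to it gives the wrong table, and departing from it takes an undocumented decision.

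A reader might also infer more than the documents support:

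- *That the per-cycle laboratory tables are wrong in the same way.* Tables 12.3.1.2 and 12.3.2.2 cite the safety population as the base but lack the sentence about distinct patients. The note can be read as naming only the analysis set, and SAP 7.6 expressly covers laboratory values. These notes are unclear, not contradictory.
- *That the SAP always names a cycle base when it uses one, so silence implies patients.* It does not. The upper panel of Table 12.1.4.1 has cycle counts under a plain percentage column, and Table 12.3.3.8 is per cycle with no denominator note.
- *That the percentages could as easily be too low as too high.* A reversal is possible, but it needs events concentrated in a few patients with unusually many cycles. Nothing in the documents points to that distribution.

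**Conclusion.** The point holds for Tables 12.2.5–12.2.8: their footnote is wrong as written, and following it would put patient incidence under a per-cycle title. On the assumed counts, the footnote basis gives about 19% to 20%, against 4.7% to 10.0% of cycles. Those figures depend on the assumed number of cycles, the assumed event pattern and the use of evaluable numbers for the safety population. The contradiction itself depends on none of them.

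Severity is minor. The tables are descriptive. The primary endpoint and the per-patient tables are unaffected, and so is the toxicity stopping rule, whose table is based on the first 10 patients in each group.

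**What to change.** Keep the present footnote for Tables 12.2.1–12.2.4. For Tables 12.2.5–12.2.8 replace it with: *N = number of cycles with the event at that worst grade; % = N divided by the cycles administered to the safety population, minus cycles with missing adverse-event information (SAP 7.6).*

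Apply the 10% filter in Tables 12.2.6 and 12.2.8 on that same denominator. Otherwise selection and printed percentage can still disagree. For example, with 90 cycles of which 5 have missing data, 9 event cycles give 9/90 = 10.0%, which is not selected, but 9/85 = 10.6%, which would be.

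As an optional clarification, state the cycle denominator under laboratory Tables 12.3.1.2, 12.3.2.2 and 12.3.3.8, with missing cycles removed separately for each laboratory parameter.

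The cost is new programming notes for four tables and a stated base for the filter in two of them. It needs no new data, patients or time.
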